9.5 Exclusion Criteria

Arm 1

Exclusion Criteria	
No	Patients will not be entered in the study for any of the following reasons
1	Involvement in the planning and/or conduct of the study (applies to staff at the study site)
2	Previous enrolment in the HYPROGEN study
3	As judged by the investigator, any evidence of severe or uncontrolled systemic disease (e.g. uncompensated respiratory, cardiac, hepatic or renal disease)
4	Evidence of any other significant clinical disorder or laboratory finding that made it undesirable for the patient to participate in the study
5	Any investigational agents or study drugs from a previous clinical study within 30 days of the first tissue collection
6	Prior treatment of localized prostate cancer including radiotherapy and/or androgen-deprivation therapy
7	Judgment by the investigator that the patient should not participate in the study if the patient is unlikely to comply with study procedures, restrictions and requirements
8	Contra-indications to MRI (incl. pacemakers etc.)
9	Bone metastases in difficult to reach areas or areas which might be at risk for pathological fracture post biopsy as judged by biopsying radiologist / chief investigator
10	Increased risk of bleeding as a result of biopsy
11	History of bleeding disorders or thrombocytopenia (platelets <100/nL)
12	Concomitant treatment with anticoagulant therapy, e.g. warfarin/low molecular weight heparin or Anti-Xa-inhibitors and other NOACs, if temporary cessation medically not justifiable
13	Current urinary tract infection (UTI) or prostatitis

Arm 2

Exclusion Criteria	
No	Patients will not be entered in the study for any of the following reasons
1	Involvement in the planning and/or conduct of the study (applies to staff at the study site)
2	As judged by the investigator, any evidence of severe or uncontrolled systemic disease (e.g. uncompensated respiratory, cardiac, hepatic or renal disease)
3	Any investigational agents or study drugs from a previous clinical study within 30 days of the first tissue collection
4	Prior treatment of localized prostate cancer including radiotherapy and/or androgen-deprivation therapy
5	Judgment by the investigator that the patient should not participate in the study if the patient is unlikely to comply with study procedures, restrictions and requirements
6	Contra-indications to MRI (incl. pacemakers etc.)

9.6 Study Payment

Patients will not receive any allowance for study participation including the provision of biopsy tissue or blood samples. However, a reimbursement of up to £40 per research visit may be requested to cover costs incurred for travel to research appointments for those patients within Arm 1 only.

9.7 Informed Consent

A member of the MDT will identify the patient at the MDT and approach the patient for possible inclusion into the study and provide the participant information leaflet either during a routine appointment to discuss the MDT recommendations or by post. All responsible consultant urological surgeons and clinical oncologists are subinvestigators of this study. Informed consent will be obtained appropriate members of the Christie urological research team at The Christie NHS Foundation Trust.

All potential study participants will be given a participant information leaflet prior to informed consent. It should be made clear to the potential trial participant that consent is voluntary and can be withdrawn without giving reasons and without prejudicing their ongoing/future care.

Potential study participants will be given adequate time to consider participation in the study based on the participant information leaflet. If the patient is willing to participate, an appointment will be made at the Christie NHS Foundation Trust within 5 working days, where the informed consent form will be signed. The patients' pimonidazole hydrochloride tablets will be dispensed from the Christie Pharmacy, if they have agreed to it and it is available. A research blood sample will also be taken at this visit.

Consent will be taken by a researcher who is a GCP trained doctor and who has been delegated by the PI to undertake this activity (and this is clearly documented on the delegation log). No study-related activities can be undertaken prior to consent.

The original, signed copy of the patient information sheet and consent form(s) will be retained in the Investigator Site File, with a copy in the patient notes. A copy will also be given to the participant.

9.8 Ineligible and Non-recruited Patients

Patients who consent to participate in the study, but who are later deemed ineligible during the screening process will be logged on the screen-failure log. Lack of inclusion in this study will in no way affect their ongoing/future clinical care.

9.9 Study Registration

Patients who have consented to participate will be assigned a unique ID code by the HYPROGEN study co-ordinator. This ID code will be used throughout their participation in the study. The master list will be held at the Urology Research Teams' office at The Christie NHS Foundation Trust.

9.10 Withdrawal of Participants

If at any time a patient expresses a wish to withdraw consent for ongoing study participation the following procedures will apply:

- Withdrawal of consent will be clearly documented in the study documentation and the study participant's medical record.
- No further clinical data will be collected from the study participant. However, existing clinical data held will be retained and used in the study.
- Samples of tissue and/or blood already collected will be retained for use in the study.
- Sample left-overs after all study-related assessments have been finished will be donated and stored anonymised at the Manchester Cancer Research Centre biobank.
- The study participant's privacy will be respected and preserved.

The investigator may also advise that a patient discontinues study participation before undergoing the biopsies, should any untoward event occur. Reasons for investigator withdrawal include (but are not limited to):

- Adverse events or acute onset of co-morbidities compromising the patient in having biopsies within the specified study criteria.
- Any start of prostate cancer treatment prior to the first biopsy / blood samples being taken.
- Severe non-compliance to this protocol.

10 DATA MANAGEMENT

The Christie **NHS**
NHS Foundation Trust

10.1 Case Report Forms

Data will be collected on paper case report forms (CRFs) and then entered into an electronic database. The database will be located at The Christie NHS Foundation Trust, and only accessible from The Christie Intranet. The database will be password protected and accessible only to those delegated to input or review the data.

10.2 Data Flow

Each participant will be assigned a trial identity code number, allocated for use on CRFs, other trial documents and any electronic spreadsheet. These documents and database will use date of birth (dd/mm/yy) and patient number.

CRFs will be treated as confidential documents and held securely in accordance with regulations. The investigator will make a separate confidential record of the participant's name, date of birth, local hospital number or NHS number, and Participant Trial Number (the Trial Recruitment Log), to permit identification of all participants enrolled in the trial in accordance with regulatory requirements and for follow-up as required.

Completion of CRFs shall be restricted to those personnel approved by the Chief or local Principal Investigator and recorded on the 'Trial Delegation Log'.

All paper forms shall be filled in using black or blue ballpoint pen. Errors shall be crossed out (but not obliterated by using correction fluid) and the correction inserted, initialled and dated. Corrections should be made legibly and initialled and dated by approved personnel. The reasons for significant changes must be provided.

If any data are not available, omissions should be indicated on the case report forms. The NHS Code of Confidentiality will be followed for this study.

Sensitive data stored on NHS or University computers will be encrypted to applicable NHS standards (AES256). The results of the study may be published in the medical literature, but patient identity will not be revealed.

10.3 Storage of Imaging and Sequencing Data

The data collected as part of the scanning procedures will be stored for fifteen years. The electronic data will be archived on computer systems managed by the Christie NHS Foundation Trust and the University of Manchester, and paper records will be stored in appropriately secure conditions. Although some personal (identifiable) data will be retained for up to five years from the day of the scan, most of the scan data itself will be anonymized shortly after the scan has taken place.

Data from nucleic acid sequencing will be anonymized, encrypted and securely stored by SciCom and for a period of 10 years.

11 ADMINISTRATIVE AND REGULATORY DETAILS

11.1 Study Sponsor

The Christie NHS Foundation Trust will act as the sponsor for this study. Delegated responsibilities will be assigned to the Chief Investigator and HYPROGEN research team to manage the study on behalf of the sponsor.

11.2 Funding Body

[name] [name], PhD (Director of the Manchester Cancer Research Centre, MCRC) using funds from the FASTMAN Centre of Excellence award (Prostate Cancer UK) and CRUK MI Leadership funds.

This study is an academic lead study that has been costed in accordance with DOH guidelines: Attributing the costs of health & social care Research & Development (AcoRD).

The study has been adopted on to the NIHR portfolio providing access to service support costs.

11.3 Peer Review

The study design, protocol and methodology were independently reviewed, discussed and approved by [name] (Clinical Trials Unit Glasgow, Beatson West of Scotland Cancer Centre, Glasgow, UK) on behalf of the National Cancer Research Institute (NCRI) Prostate Clinical Study Group (CSG) and [name] (Medical Oncology Department, Guy's and St. Thomas' NHS Foundation Trust, London, UK).

11.4 Patient and Public Involvement

To provide easily understandable and patient centred study materials, e.g. participant information leaflet and consent form, a prostate cancer patient representative ([name]) has reviewed and approved these documents and was involved in study design discussion. The patient is completely independent from the sponsor, funder and all investigators of the study.

11.5 Ethical Approval

No patients will be entered onto the study before ethical approval has been confirmed. The study protocol has received the favourable opinion of the HRA Ethics Committee for the study protocol, informed consent forms and other relevant documents.

The study will be conducted in accordance with, but not limited to, the Human Rights Act 1998, the Data Protection Act 2018, Freedom of Information Act 2000 subject to the provisions of sections 41 and 43 thereof, the EU Clinical Trials Directive, the Human Tissue Act 2004, ICH GCP E6 R2 addendum, the Declaration of Helsinki 1996, Ionising Radiation Medical Exposure Regulations (IRMER), and the UK Policy framework for Health and Social Care research as amended from time to time.

Where patients agree to take part in the study, they will be informed of how data are recorded, collected, stored and processed and may be transferred to other countries, in accordance with The General Data Protection Regulation (GDPR) (EU) 2016/679. As the sponsor of the study trial is a non-commercial organisation the legal basis for the handling and processing of data is 'task in the public interest'.

Annual progress reports will be submitted to REC within 30 days of the anniversary date on which the favourable opinion was given, and annually until the study is declared ended.

11.6 Confidentiality

All Investigators and site staff involved with the study must comply with the requirements of General Data Protection Regulations 2018 with regard to the collection, storage, processing and disclosure of personal information and will uphold the Act's core principles.

[name], Managing Director (Research, Innovation and Education) at The Christie NHS Foundation Trust will act as the custodian of the data collected in this study. [name] will act as the custodian for the samples collected during the study.

Key principles include:

- The research team will have access to the clinical data for the purpose of this study. Study data may be inspected by individuals from the sponsor or regulatory authorities for monitoring and audit purposes. Informed consent will be obtained to cover this activity.
- Any personal data recorded will be regarded as confidential, and any information which would allow individual patients to be identified will not be released into the public domain.

- Appropriate storage, restricted access and disposal arrangements for patient's personal and clinical details. Patient's notes and study files will be held in a secure storage area with limited access. Computers used to collate data will have limited access measures via usernames and passwords.

11.7 Protocol Compliance

The study protocol must be adhered to at all times. Intentional deviations from the protocol are not permitted under any circumstances.

Accidental protocol deviations must be reported to the Chief Investigator and the sponsor. Recurring deviations will be investigated by the sponsor to deem if it can be classed as a serious breach.

Identified/suspected serious breaches of the study protocol or GCP will be notified to the Operational Director of Research, or Quality Manager via: [name], [contact].

The R&D Sponsor Team will be notified of other deviations significantly impacting the risk profile of the study or significantly interrupting study services or supplies via: [name], [contact].

Minor deviations should be monitored by the research team for seriousness and trends. Sponsor shall maintain oversight of these through periodic sponsor oversight activity reports (SOAR) and review of trial management group minutes.

11.8 Trial Monitoring

A trial monitoring plan will be developed and agreed by the research team and the sponsor. The procedures and anticipated frequency will be based on the trial risk assessment.

11.9 Study Oversight

The safety of this study is being over seen by the Safety Review Committee (SRC) which will be under the chairmanship of the Chief Investigator and will comprise of the co-investigators and study co-ordinator. The committee will meet to review the study conduct over the first five and ten patients enrolled.

A Trial Management Group (TMG) will be established and will include those individuals responsible for the day to day management of the study including the Chief Investigator, Co-investigators and study managers as detailed in the key study contacts section of this protocol. Meetings will take place after inclusion of the fifth and tenth patient and every 3 months thereafter in order to evaluate recruitment and feasibility of the study

interventions and to optimise study procedures by developing protocol amendments, if needed.

Key findings/decisions from these meeting will be notified to the sponsor as soon as possible.

Sponsor shall maintain oversight of the study conduct through

- Reviews of Annual Progress Reports (APR).
- Periodic sponsor oversight activity reports (SOAR) by the research team.
- Reviews of Trial Management Group and Safety Review Committee minutes.

11.10 Protocol Amendments

Any changes in research activity will require an amendment and will be initiated by the Chief Investigator. Proposed changes must be submitted in writing to the sponsor. The amendment will be categorised as substantial or non-substantial.

Any required changes to the documents that supported the original ethical approval will be submitted as an amendment to the appropriate ethical and regulatory authorities by the research team. Substantial amendments will not be implemented until the HRA and REC grant approval.

For any amendments that will affect a participating site's local capability and capacity, the research team will confirm with each participating sites R&D department that local capability and capacity is ongoing.

An Urgent Safety Measure (USM) may be put in place with immediate effect without gaining prior authorisation by the REC in order to protect clinical trial participants from any immediate hazard to their health and safety. USMs must be approved by the sponsor prior to implementation however REC and HRA must be notified by substantial amendment within 3 days of the measures being taken.

11.11 Liability and Indemnity

As the Chief Investigator ([name]) is a member of staff of the University of Manchester, study insurance will be covered under the University's policy for Medical Malpractice Errors and Omissions.

As the sponsor, The Christie NHS Foundation Trust, is an NHS organization, the NHS indemnity scheme will apply in the event of harm to participants arising from the conduct or management of the study.

The Christie **NHS**
NHS Foundation Trust

11.12 Adverse Events and Adverse Reactions

The study does not involve any drug/device treatment (androgen deprivation and/or chemotherapy is given after the end of study as part of clinical routine care or a subsequent clinical trial unrelated to this study) and all procedures performed are part of standard clinical practice. Pimonidazole hydrochloride is used as a hypoxia marker substance without any known side effects at the prescribed dose of 0.5 g/m².

Adverse events following the biopsy visit should be monitored as per standard of care by the local urology on call team at the study site where the biopsies have been taken.

Adverse events do not need to be recorded on the CRF unless they affect study biopsy collection or study participation. Any adverse events which do not affect a patients' participation in this study, will not be recorded.

A Serious Adverse Event (SAE) is any untoward medical occurrence in a study patient that:

- Requires inpatient hospitalisation or prolongation of existing hospitalisation.
- Results in persistent or significant disability/incapacity, or
- Is a congenital anomaly/birth defect
- Is life threatening
- Results in death

We do not anticipate any serious adverse events. However, any AEs meeting the definition of a Serious Adverse Event (SAE) must be reported to the CI/delegated research staff using the trial specific SAE Report Form immediately, and within 24 hours of observing or learning about the event. As many sections of the SAE form should be completed as possible (with further information being provided as it becomes available).

The CI will be responsible for reviewing the reports for:

- Completeness
- Causal link to the study procedures
- Expectedness

The Sponsor will be notified by the CI/delegated research staff through [contact] if an SAE is identified as related to the study and is unexpected (SUSAR). Identified SUSARs will be reported (by the CI/ delegated research staff) to the relevant REC within 15 days of becoming aware of the event, using the HRA Non-CTIMP Safety Report Form.

SAEs will only be collected up to 30 days after the last biopsy sample is taken. All SAEs must be followed-up until resolution and site investigators must provide follow-up SAE reports if the SAE had not resolved at the time the initial report was submitted.

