Biopsies of the prostate are part of normal regular care performed on all patients with *de novo* metastatic PCa. As for routine diagnostic purposes, prostate biopsies will be done though the perineum guided by trans-rectal ultrasound (TRUS) targeting lesions, which may have already been identified in the pre-study diagnostic multiparametric MR scan of the prostate (if available). Preferably, routine diagnostics and research sampling will be undertaken during the same biopsy procedure. However, if a diagnostic TRUS biopsy of the prostate has been performed before, the research biopsy will require an additional intervention surplus the bone biopsies and the blood sampling, which are not part of routine diagnostics and thus cannot be seen as standard of care. If a second prostate biopsy solely for research purposes is denied by the patient, only a bone biopsy and a blood sample will be taken. Importantly, the techniques of image-guided biopsy taking are routinely done for the diagnosis and management of patients with different types of cancers and thus safely applicable. As part of the HYPROGEN study, the bone biopsies will be used to histologically confirm the diagnosis of metastatic disease in a radiographically bone metastatic stage.

Most side effects associated with the medical procedures in this study are expected to be mild to moderate and to disappear after a short time. The main risks related to the HYPROGEN study interventions comprise the following:

Pain or Discomfort

Biopsies involve needle tests of deeper tissues and can cause pain or discomfort both at the time of the biopsy and also for up to several days after the biopsy. Local anaesthetics injection will be given for both the prostate biopsies as well as the bone biopsies to numb the respective site as good as possible to reduce the possible discomfort. The local anaesthetic injection itself may cause some temporary pain or burning sensation until the onset of numbness, and as the anaesthetics wear off pain may re-appear. Simple systemic analgesics such as paracetamol may be advised if pain occurs as a result of the biopsies.

Bleeding or Bruising

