Any needle test can be associated with bleeding or bruising. Blood clotting will be assessed during the screening process and patients will not proceed to the biopsy visit if they appear to be at higher bleeding risk than normal. Anticoagulant treatment will be halted if medically justifiable. Biopsies close to higher risk areas such as large blood vessels will be avoided. However, despite these precautions, rarely the bleeding from biopsies can cause significant blood loss or risk to life.

Infections

Patients are vulnerable to infection while having a biopsy or blood sample taken. Minor infections can become life-threatening. Symptoms of infection include fever, shivering, sweats, sore throat, diarrhoea, dysuria, haematuria, cough or breathlessness. Patients will be asked to measure the core body temperature on the days after the biopsy visit and to report any febrile temperatures or signs of infection immediately to the study staff or via The Christie Hotline under [name], which is open 24/7.

All patients undergoing a transperineal prostate biopsy will receive antibiotic prophylaxis as per local policy for prophylactic antibiotic treatment for prostate biopsies.

Arm 2

This is a prospective, translational, exploratory biomarker study, and it is unlikely to directly benefit the participants of this study. However, the results of this study may provide benefit for prostate cancer patients in the future.

Participants will take an oral pimonidazole tablet prior to their radical prostatectomy as part of the study. Oral pimonidazole at a dose of 0.5 g/m² has been well tolerated without any signs of toxicity.

Participants in Arm 2 agreeing to additional imaging will undergo 2 additional MRI scans during which they will receive intravenous gadolinium contrast and be asked to breath 100% oxygen through an oxygen mask.

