8.7 Blood Sampling

For patients in Arm 1 - A blood sample for research purposes will be withdrawn at the each of the following visits:

(i) Baseline visit (pre- pimonidazole)

- 2 x 10mL *Streck cell-free DNA blood collection tubes*® for circulating tumour cell (CTC) collection and circulating tumour DNA (ctDNA) extraction.
- 1-2 x 3.5mL blood samples collected into EDTA tubes for germ line DNA extraction and processing to PBMC for banking and future profiling of immune cell populations
- 1 x 10mL serum tubes for future, biobank related research projects, ie lipidomics, metabolics and microRNA analysis

(ii) Biopsy visit (pre-biopsy)

- 2 x 10mL *Streck cell-free DNA blood collection tubes*® for circulating tumour cell (CTC) collection and circulating tumour DNA (ctDNA) extraction.
- 1 x 10mL serum tubes for future, biobank-related research projects, ie lipidomics, metabolics and microRNA analysis

(iii) Follow up visit (within 6 months post-treatment, for patients 11-30)

- 2 x 10mL *Streck cell-free DNA blood collection tubes*® for circulating tumour cell (CTC) collection and circulating tumour DNA (ctDNA) extraction.
- 1-2 x 3.5mL blood collected into EDTA tubes for germline DNA extraction and processing to PBMC for banking and future analysis of immune cell populations
- 1 x 10mL serum tubes for future, biobank related research projects, ie lipidomics, metabolics and microRNA analysis

For Patients in Arm 2

A blood sample (maximum 20ml) will be taken for standard of care blood tests prior to prostatectomy including Full Blood Count, Renal Function and PSA. At the same time these standard of care bloods are taken, additional bloods - a maximum of 30ml – will be taken for research purposes as required for the following downstream analysis:

- Germ line DNA extraction and optional processing to PBMC for banking and future profiling of immune cell populations
- Biobank related research projects, ie lipidomics, metabolics and microRNA analysis

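### Section 11.12 leaves most non-serious complications of the research biopsies without a systematic study record, on a premise that Section 8.3 contradicts

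*Protocol*

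**What the plan says.** Protocol Section 11.12 has two consecutive sentences on non-serious adverse events. The first: "Adverse events do not need to be recorded on the CRF unless they affect study biopsy collection or study participation". The second: "Any adverse events which do not affect a patients' participation in this study, will not be recorded". The section supports this light collection by stating that "all procedures performed are part of standard clinical practice". It places follow-up outside the study: "Adverse events following the biopsy visit should be monitored as per standard of care by the local urology on call team". Serious adverse events are treated differently. They go on a trial form within 24 hours, are collected up to 30 days after the last biopsy sample, and are followed to resolution.

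Section 8.3 describes the bone biopsies, and a second prostate biopsy done solely for research, as procedures "which are not part of routine diagnostics and thus cannot be seen as standard of care". It names pain, bleeding or bruising, and infection as the main risks, and expects most side effects to be mild to moderate and brief. Men are asked to "report any febrile temperatures or signs of infection immediately to the study staff" or to a hotline.

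Section 11.9 gives safety oversight to the Safety Review Committee (SRC): "The committee will meet to review the study conduct over the first five and ten patients enrolled". It asks the Trial Management Group (TMG) to judge the feasibility of the interventions and to improve procedures by amendment.

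**The concern.** The recording rule depends on whether an event disturbs the study, not on whether a study procedure caused it. Research biopsies are the main physical burden that Arm 1 adds, and their expected complications are of the kind that rarely disturbs anything later in the schedule. A fever treated without admission, or a bleed that settles at home, can be reported to study staff as instructed and still need no entry on the CRF.

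Two things are at stake. The SRC and TMG are to review early patients and adjust procedures, and they would do so without a systematic listing of the complications the protocol itself expects. At the end, the study could not state how often its research procedures caused non-serious harm. A short list of events would reflect the recording rule and could be misread as good tolerability.

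**Working it through.** The protocol states no complication rate, so there is no figure of its own to reproduce. The check is mainly textual.

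**1. The two recording sentences compared (Section 11.12).**

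| Event affects collection | Event affects participation | First sentence | Second sentence |
|---|---|---|---|
| yes | yes | record | no bar |
| no | yes | record | no bar |
| yes | no | record | do not record |
| no | no | need not record | do not record |

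The third row is a contradiction. In the fourth row the first sentence leaves recording optional and the second rules it out.

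**2. The premise (Section 11.12 against Section 8.3).** Section 11.12 treats all procedures as standard practice. Section 8.3 says the opposite of the bone biopsies and of a research-only prostate biopsy. The added sampling is not trivial. Section 8.4 allows two bone sites with three specimens each (2 × 3 = 6), and Section 8.5 allows a maximum of 8 to 12 prostate cores beyond those needed for care.

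**3. When an event could still meet the rule.**
- *During sampling.* Pain or bleeding at one procedure can curtail or prevent the next. Such an event affects collection and meets the first sentence.
- *After sampling.* Collection can no longer be affected, so only participation counts. What remains is the whole-body MRI, if not already done (Section 8.2 puts it in the 10-15 working days after biopsy; Section 8.8 also allows it before), and the follow-up visit at 3-6 months. The Section 5 table shows a physical examination at follow-up for all Arm 1 men; only the research blood draw is limited to patients 11-30.

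Section 8.3 expects most side effects to be short-lived, with pain lasting up to several days. Some could disturb an early MRI appointment; few would reach a visit months later. Most post-biopsy complications therefore fall in the fourth row of the table.

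**4. Illustration of what the SRC would see (all rates assumed).**
- Expected number of affected men among the 30 in Arm 1: 30 × 0.05 = 1.5; 30 × 0.20 = 6; 30 × 0.50 = 15.
- Chance that at least one of ten biopsied men is affected, 1 − (1 − p)^10:

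| Type of event | Assumed p | Chance in ten men |
|---|---|---|
| Non-serious complication | 5% | 40.1% |
| Non-serious complication | 20% | 89.3% |
| Non-serious complication | 50% | 99.9% |
| Serious adverse event | 1% | 9.6% |
| Serious adverse event | 2% | 18.3% |
| Serious adverse event | 5% | 40.1% |

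- If no serious event is seen in ten men, the exact one-sided 95% upper bound on the true rate is 1 − 0.05^(1/10) = 25.9%.

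Section 11.12 anticipates no serious events, so non-serious complications are the more likely early signal, and they are the ones the rule mostly leaves out.

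**The case against.** It can be said in the plan's favour that selective recording is a legitimate choice in an exploratory study reported through the non-CTIMP route. None of the research aims in Section 7 is a complication rate, and Section 9.2 uses the word feasibility only to explain why there is no power calculation. Section 8.3 calls the biopsy techniques routine. The SRC is made up of the chief investigator, co-investigators and co-ordinator, so its members may hear of events that never reach the CRF.

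Much of this stands. The routine technique softens the conflict with Section 8.3 but does not remove it, because that section still places these biopsies outside standard of care. Informal knowledge among the investigators is not a record that can be counted or reported.

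Two stronger readings are tempting, and the protocol does not support either.
- *That the SRC has nothing to review.* It still has every serious event in the 30-day window, events that affect collection or participation, withdrawals (Section 9.10 lists adverse events that compromise biopsy as a reason) and study conduct.
- *That no non-serious post-biopsy event could be recorded for the first ten men if their MRI came first.* The limit to patients 11-30 applies to the blood draw: "Follow up visit (within 6 months post-treatment, for patients 11-30". The Section 5 table and Sections 8.2 and 8.3 describe a follow-up visit for Arm 1 without that limit, so some participation remains to be affected.

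**Conclusion.** The point holds as a gap in data collection created by a stated rule. The two sentences in Section 11.12 disagree with each other, their premise conflicts with Section 8.3, and under either sentence most non-serious complications arising after the biopsies need no study record. The SRC's safety data would be sparse, not empty.

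That most are missed is an inference from the protocol's own description of timing and severity. The exact share cannot be given without complication rates. The counts of 1.5 to 15 affected men rest on assumed rates of 5% to 50% and only show scale; the conclusion does not depend on them. No sample size or planned efficacy-type analysis changes. The change should be made: it is inexpensive, and complications not captured at the time are hard to recover later.

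**What to change.** **Section 11.12.** Remove or correct the statement that all procedures are standard practice, so that it agrees with Section 8.3. Replace both recording sentences with one rule: every adverse event possibly related to a research biopsy or to pimonidazole goes on the CRF, whether or not it affects collection or participation. In Arm 1, use the 30-day post-biopsy window that already applies to serious events. Arm 2 men are also offered pimonidazole but have no study biopsy, so that window has no starting point for them; state a separate one that runs from pimonidazole intake.

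**Section 11.9.** Say that the SRC receives this listing. Count its two safety reviews as the fifth and tenth Arm 1 men who have had a research biopsy. As worded, the count of enrolled patients does not name an arm and could include Arm 2 men who have had no study biopsy.

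**Cost.** One CRF page, wording changes in two sections and a little data entry. Men are already asked to report fever and signs of infection, so that part adds no new contact with patients.
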